2.3 Exploratory objectives

2.3.1 Exploratory objectives specific to efficacy-estimating substudies

- To describe the type of *FGFR1-3* GAs in responders and non-responders
- To explore the concordance between molecular *FGFR* assessments from plasma-based and tissue-based NGS testing
- To explore the efficacy of derazantinib-atezolizumab in combination following documented disease progression in patients who previously received derazantinib monotherapy and crossed over to combination treatment (Substudy 4)
- To explore the efficacy of derazantinib-atezolizumab in combination by iRECIST (see Section 5.3.3.2.4) as measured by ORR, DCR, DOR and PFS
- To compare the efficacy of derazantinib with that of derazantinib-atezolizumab in combination to generate potential hypotheses for future comparative studies (Substudy 4)
- To explore the efficacy of derazantinib and of derazantinib-atezolizumab in combination by response-indicating molecular biomarkers, as measured by ORR, DCR, DOR, PFS and OS
- To explore the effect of derazantinib on CSF1R expressing cells in blood samples and skin biopsies
- To characterize utilities in patients treated with derazantinib or derazantinib-atezolizumab in combination using the EQ-5D (5L) for health economic modeling.

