8.1.3 Substudy 4, Cohorts 4a and 4b

For both cohorts within Substudy 4, the null hypothesis that the true ORR is $p_0 \leq 0.07$ will be tested against a one-sided alternative. In Stage 1 of each cohort, 16 evaluable patients will be enrolled. If 1 or fewer patients with an objective response are observed in these 16 patients, the cohort will be stopped. If 2 or more patients with an objective response are observed, an additional 34 patients will be enrolled for a total of 50. The null hypothesis will be rejected if seven or more responses are seen in these 50 patients. Type I error rate is 0.0448 and power is 0.8027 when true ORR is $p_1 = 0.20$.

The ORR of 7% for the null hypothesis reflects the ORR reported based on literature of retrospective data and/or small cohorts of uncontrolled studies (Di Lorenzo 2015, Soga 2010) for *FGFR1–3* GA expressing UC patients treated with third or fourth-line single-agent chemotherapy with prior progression following platinum-containing chemotherapy, immune-checkpoint blockade and/or FGFR inhibitor treatment.

8.1.4 Substudy 5

The Fleming's two-stage design sample size calculation is based on the assumption that patients with mUC expressing *FGFR1-3* GAs, after failure of prior platinum- or immune-checkpoint-inhibitor-containing treatment, treated with 200 mg BID derazantinib will attain a clinically meaningful ORR of approximately 30%. This is similar to that obtained with erdafitinib for this patient population, and considered the benchmark by oncology experts. An ORR of 10% is not considered sufficiently effective to warrant further clinical investigation.

Using a two-stage Fleming design, a total sample size of 26 is required to test a null hypothesis of $H_0: \pi \leq 0.1$ versus an alternative hypothesis of $H_a: \pi \geq 0.3$ with a one-sided target significance level of 0.05 and target power of 80%, where π is the true proportion of successes. This design results in an exact type 1 error rate of 0.039, an exact level of power of 81.9%, an average sample number of 18 patients under H_0 and of 21 under H_a . [Table 8](#) summarizes the required samples sizes and required responses to either accept or reject H_0 .

Table 8 Summary of sample size and required responses of proposed two-stage Fleming design

	Sample size	Responders to accept H_0		Responders to reject H_0	
	N	N	%	n	%
Stage 1	13	1	7.7	5	38.5
Stage 2	26	5	19.2	6	23.1

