As of Protocol Version 5.0, this substudy has been modified. First-line cisplatin-ineligible patients with mUC expressing FGFR1–3 GAs are to be treated with derazantinib 200 mg BID and atezolizumab 1200 mg Q3W in combination, with the co-primary objectives of assessing the safety and efficacy of this regimen in this patient population. If derazantinib 200 mg BID at the SIA is not assessed as safe and tolerable, patients are to be treated with the RP2D determined in Substudy 2. Substudy 3 uses a Fleming's two-stage design. A total sample size of 36 is required to test a null hypothesis of $H_0: \pi \leq 0.25$ versus an alternative hypothesis of $H_a: \pi \geq 0.45$, where π is the true proportion of successes. See Section 6.1.6.3 for details regarding the required sample size and required responses to either accept or reject H_0 .

3.3. Substudy 4

This substudy will enroll FGFR inhibitor-resistant patients with mUC expressing FGFR1–3 GAs. Patients in this substudy are to be randomized (1:1) into two non-comparative groups: Cohort 4a patients will receive derazantinib 300mg QC monotherapy, and Cohort 4b patients will receive derazantinib 300mg QC and atezolizumab 1200 mg Q3W in combination. The primary objective of this substudy is to assess the efficacy

of derazantinib monotherapy and derazantinib-atezolizumab in combination in this patient population. Randomization will be based on a computer-generated randomization schedule via IWRS and will be stratified for key prognostic factors. The presence of visceral metastasis, an ECOG PS of 2, or a preceding FGFR inhibitor treatment interval of less than 6 months (i.e., less than 24 full weeks) will be credited with one point, and patients will be stratified according to their composite score values of 0–1 versus 2–3 points.

Substudy 4 uses a Simon's two-stage design. In Stage 1, 16 evaluable patients will be enrolled for both cohorts. If 1 or fewer patients with an objective response are observed in these 16 patients, the cohort will be stopped. If 2 or more patients with an objective response are observed, an additional 34 patients will be enrolled for a total of 50 patients. The null hypothesis will be rejected if 7 or more responses are seen in these 50 patients.

3.4. Substudy 5

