6.1.6.4. Substudy 4, Cohorts 4a and 4b

For both cohorts within Substudy 4, the null hypothesis that the true ORR is $p_0 \leq 0.07$ will be tested against a one-sided alternative. In Stage 1 of each cohort, 16 evaluable patients will be enrolled. If 1 or fewer patients with an objective response are observed in these 16 patients, the cohort will be stopped. If 2 or more patients with an objective response are observed, an additional 34 patients will be enrolled for a total of 50. The null hypothesis will be rejected if seven or more responses are seen in these 50 patients. Type I error rate is 0.0448 and power is 0.8027 when true ORR is $p_1 = 0.20$.

The ORR of 7% for the null hypothesis reflects the ORR reported based on literature of retrospective data and/or small cohorts of uncontrolled studies ([Di Lorenzo 2015](#), [Soga 2010](#)) for FGFR1–3 GA expressing UC patients treated with third or fourth-line single-agent chemotherapy with prior progression following platinum-containing chemotherapy, immune-checkpoint blockade and/or FGFR inhibitor treatment.

6.1.6.5. Substudy 5

The Fleming’s two-stage design sample size calculation is based on the assumption that patients with mUC expressing FGFR1–3 GAs, after failure of prior platinum- or immune checkpoint- inhibitor-containing treatment, treated with 200 mg BID derazantinib will attain a clinically meaningful ORR of approximately 30%. This is similar to that obtained with erdafitinib for this patient population, and considered the benchmark by oncology experts. An ORR of 10% is not considered sufficiently effective to warrant further clinical investigation.

Using a two-stage Fleming design, a total sample size of 26 is required to test a null hypothesis of $H_0: \pi \leq 0.1$ versus an alternative hypothesis of $H_a: \pi \geq 0.3$ with a one-sided target significance level of 0.05 and

target power of 80%, where π is the true proportion of successes. This design results in an exact type 1 error rate of 0.039, an exact level of power of 81.9%, an average sample number of 18 patients under H_0 and of 21 under H_1 . Table 3 summarizes the required samples sizes and required responses to either accept or reject H_0 .

Table 3: Sample size and required responses of proposed two-stage Fleming design (Substudy 5)

	Sample size	Responders to accept H_0		Responders to reject H_0	
	N	n	%	n	%
Stage 1	13	1	7.7	5	38.5
Stage 2	26	5	19.2	6	23.1

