the first 18 patients). Posterior estimates of the probability that the response rate exceeds 0.25 will also be calculated assuming a non-informative prior distribution. A prior distribution Beta(1,1) will be used as a vague, non-informative prior, giving a uniform distribution with mean of 0.5 response rate with wide uncertainty. This will be multiplied by a likelihood with distribution Beta(a,b) where a is the number of responses and b is the number of non-responses, to obtain the posterior distribution from which the probability that the response rate exceeds 0.25 will be estimated. This analysis will only consider BICR assessed response within the mITT population.

Substudy 4

$H_0: p \leq 0.07$ versus $H_A: p \geq 0.20$

If there are one or zero patients with an objective response (defined as a confirmed CR or PR) in the first 16 evaluable patients included in the interim analysis in each of Cohort 4a and 4b, the cohort will be stopped. If not, an additional 34 patients will be enrolled, for a total of 50 evaluable patients. The null hypothesis will be rejected if 7 or more objective responses are observed in these 50 patients.

Comparisons between cohorts will be descriptively summarized by reporting the difference in point estimates between cohorts, with a 2-sided exact 95% CI for the difference and a p-value from a Fisher exact test.

Substudy 5

$H_0: p \leq 0.10$ versus $H_A: p \geq 0.30$

If there is one or fewer patient with a response (defined as a CR or PR) in the first 13 evaluable patients included in the interim analysis, the cohort will be stopped. If not, an additional 13 patients will be enrolled, for a total of 26 evaluable patients. The null hypothesis will be rejected if six or more responses are observed in these 26 patients (or if five or more responses are observed in the first 13 patients). Posterior estimates of the probability that the response rate exceeds 0.1 will also be calculated assuming a non-informative prior distribution. This analysis will only consider BICR assessed response within the mITT population.

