the 2-sided 95% CIs around the percentiles will be presented. Kaplan-Meier estimates at 3, 6, 9 and 12 months will also be presented. The Kaplan-Meier survival curves will also be presented. For substudy 4 comparison between cohorts will be made by considering a hazard ratio, with associated 2-sided 95% confidence interval and p-value, from an unadjusted Cox proportional hazards model.

The date of cohort assignment by IWRS, first dose, disease progression, death, last tumor assessment and PFS days will be reported in a by-patient listing.

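### When only one Substudy 4 cohort continues past Stage 1, the SAP's exploratory 4a-versus-4b comparisons mix randomised patients with up to 34 who could not have been randomised

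*SAP*

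**What the plan says.** SAP 3.3 describes the allocation: "Patients in this substudy are to be randomized (1:1) into two non-comparative groups". Protocol 4.4.3 adds that this is done through IWRS, stratified by a prognostic composite score.

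The two-stage rule is set for each cohort separately (Protocol 8.1.3; SAP 6.1.6.4): "In Stage 1 of each cohort, 16 evaluable patients will be enrolled", and "If 1 or fewer patients with an objective response are observed in these 16 patients, the cohort will be stopped". Otherwise "an additional 34 patients will be enrolled for a total of 50". For the final test, "The null hypothesis will be rejected if seven or more responses are seen in these 50 patients".

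SAP 6.3 places all efficacy analyses on the mITT population and says that Substudy 4 comparisons are descriptive and only for generating hypotheses. The mITT definition (SAP 5.2) has no condition on stage or concurrent randomisation. Within that set:

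- ORR (SAP 6.3.1.1): "Comparisons between cohorts will be descriptively summarized by reporting the difference in point estimates between cohorts", with an exact 95% CI and a Fisher p-value. DCR (6.3.2.1) is handled in the same way.
- PFS (6.3.2.3): "For substudy 4 comparison between cohorts will be made by considering a hazard ratio", with a CI and p-value from an unadjusted Cox model. DOR (6.3.2.2), OS (6.3.2.4) and TTP (6.3.3.1) are handled alike.

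The Substudy 4 subgroups in SAP 6.3.3.2 cover the stratification score and its components, not enrolment period. Neither document says how patients are assigned after one cohort has closed.

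**The concern.** Once one cohort closes, only one treatment is open and 1:1 randomisation cannot continue. Patients enrolled after that have no concurrent randomised counterpart. Pooling them into a 4a-versus-4b difference or hazard ratio mixes the treatment contrast with anything that changes over calendar time, such as case mix, sites, or knowledge that the other cohort failed. The unadjusted Cox model has no term for stage or time.

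At stake is how an exploratory result is read. Comparing the two treatments to generate hypotheses for later trials is a listed exploratory objective (Protocol 2.3.1). A p-value or hazard ratio from two cohorts described as randomised is easily taken as randomised evidence, with nothing in the output to show that part of it is not.

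**Working it through.** **Inputs** (Protocol 8.1.3; SAP 6.1.6.4): Stage 1 n = 16, stop at ≤1 response; Stage 2 adds 34, total 50; reject at ≥7; null ORR 0.07, alternative 0.20.

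**The plan's own figures.** P(reject) = Σ over x ≥ 2 of Bin(x; 16, p) × P(Bin(34, p) ≥ 7 − x). This gives 0.0448 at p = 0.07 and 0.8027 at p = 0.20, matching the stated type I error and power.

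**Chance that a cohort stops.** P(X ≤ 1 | n = 16) = (1−p)^16 + 16p(1−p)^15 = 0.690 at 7% and 0.141 at 20%.

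**Chance that exactly one stops.** With independent cohorts and stopping probabilities a and b, this is a(1−b) + b(1−a):

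| True ORRs | Calculation | Exactly one stops |
|---|---|---|
| 7% and 7% | 2 × 0.690 × 0.310 | 0.43 |
| 7% and 20% | 0.690 × 0.859 + 0.141 × 0.310 | 0.64 |
| 20% and 20% | 2 × 0.141 × 0.859 | 0.24 |

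The same formula gives 0.50 if both are 10% and 0.41 if both are 15%.

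**Share not concurrently randomised.** The comparison is then 16 v 50. With no overrun the share is 34/50 = 68% of the continuing cohort and 34/66 = 51.5% of all compared patients. Suspension of enrolment at the interim is optional (SAP 6.1.6), so more patients may be randomised before a stop decision. The documents give no number. With an assumed k extra per cohort the shares are (34−k)/50 and (34−k)/(66+k):

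| k | Of continuing cohort | Of all compared |
|---|---|---|
| 0 | 68% | 51.5% |
| 2 | 64% | 47% |
| 4 | 60% | 43% |
| 8 | 52% | 35% |

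**Effect of drift.** If the underlying ORR shifted between stages by an assumed 5, 10 or 15 points, the difference would move by 0.68 × shift = 3.4, 6.8 or 10.2 points.

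**Would restricting ORR to concurrent patients help?** When exactly one cohort stops, the concurrent data are ≤1/16 against ≥2/16. With equal true ORR p, the expected spurious difference is:

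- restricted, 16 v 16: E[X | X≥2]/16 − E[X | X≤1]/16
- full, 16 v 50: (E[X | X≥2] + 34p)/50 − E[X | X≤1]/16

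At p = 0.07, E[X | X≤1] = 0.546 and E[X | X≥2] = 2.398. Restricted: 0.1499 − 0.0341 = 11.6 points. Full: (2.398 + 2.38)/50 − 0.0341 = 6.1 points.

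At p = 0.20, the two means are 0.800 and 3.593. Restricted: 0.2246 − 0.0500 = 17.5 points. Full: (3.593 + 6.8)/50 − 0.0500 = 15.8 points.

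Restriction therefore makes the selection bias in ORR larger, because the Stage 2 patients dilute it.

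**The case against.** The strongest objection is that this is a limited exploratory comparison. The cohorts are labelled non-comparative, SAP 6.3 confines the comparison to hypothesis generation, and the primary question for each cohort is its own ORR against 7%. That stands and it caps the importance. It does not remove the problem, because the SAP still specifies p-values and hazard ratios between the cohorts, and a hypothesis for a later comparative trial needs a contrast that can be interpreted.

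SAP 6.3.2.3 and 6.3.2.4 also list each patient's IWRS assignment date, so the concurrent patients can be identified. That makes a remedy easy, but no planned analysis uses it.

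A reader might infer more than the documents support:

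- *That the comparison will usually be compromised.* Of the three main scenarios only one exceeds 50%. If both cohorts stop or both continue, this lone-cohort phase does not arise.
- *That most compared patients will be non-randomised.* The overall share is 51.5% with no overrun and falls below half with two extra randomised patients per cohort.
- *That randomisation and stratification were put in to support this comparison.* Protocol 4.4.3 gives no such reason.
- *That every later patient enters the open cohort.* This is a reasonable inference, but neither document states it.
- *That restricting every contrast to concurrent patients is the cure.* For ORR it is not: the sign is fixed by the stopping rule and the bias grows.

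**Conclusion.** The concern holds as a gap in the exploratory analysis. Stopping is per cohort, the between-cohort comparisons use the whole mITT set, and nothing deals with the case in which one cohort continues alone. That case has probability 0.24 to 0.64 in the three main scenarios, with true ORRs of 7% or 20%. In it, up to 68% of the continuing cohort lacks a concurrent randomised comparator.

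This assumes independent cohorts, no overrun for the 68%, and later patients entering the open cohort. Use of all of 4a against all of 4b is inferred from the mITT rule and the absence of any restriction. The size of any time-related confounding is unknown; the drift figures are an assumed range. The single-arm decision rules and their error rates are unaffected.

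**What to change.** In SAP 6.3.1.1, 6.3.2.1 to 6.3.2.4 and 6.3.3.1, add a rule for the case in which only one cohort continues to Stage 2:

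- Report each cohort's full results separately, with no between-cohort p-value for any endpoint.
- Limit any PFS, OS or TTP hazard ratio to patients randomised by IWRS while both cohorts were open.
- Do not add an ORR test on that restricted set. Label any ORR difference shown as affected by futility selection.

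The SAP should also state how patients are assigned once one cohort has closed.

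The cost is SAP wording and one flag based on assignment date, with no change to conduct or to the primary rules. The exploratory time-to-event contrast will have fewer patients. Little is lost with the ORR p-value: at 16 v 50, ignoring selection, Fisher power for 7% against 20% is about 10% (two-sided 0.05). Selection from the futility rule remains in whatever contrast is shown and should be acknowledged beside it.

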6.3.2. Secondary Efficacy Variable(s)

6.3.2.1. Disease Control Rate (All Substudies)

Disease Control Rate (DCR) is defined as the proportion of patients achieving a confirmed CR or PR or stable disease (SD) (or Non-CR/Non-PD for patients with non-measurable disease) using RECIST 1.1 as assessed by BICR. Point estimates and exact 2-sided 95% CIs will be provided. Comparisons between cohorts of substudy 4 will be descriptively summarized by reporting the difference in point estimates between cohorts, with a 2-sided exact 95% CI for the difference and a p-value from a Fisher exact test.

6.3.2.2. Duration of Response (All Substudies)

Duration of Response (DOR) will be calculated from the first date of documented objective tumor response (confirmed CR or PR) to the date of disease progression as assessed by BICR or death. If a patient is discontinued or lost to follow-up with no documentation of PD, DOR is defined as the time from the date of first documented objective tumor response to the date of last tumor assessment as a censored value. PD or death post end of treatment will be censored at date of last tumor assessment as a censored value.

DoR will be derived only for patients who have the best overall response of CR or PR.

DOR will be analyzed using Kaplan-Meier methodology ([Kaplan & Meier 1958](#)). The median DOR will be presented along with the standard error and 2-sided 95% CI. If they are calculable, the 25th and 75th percentiles and the 2-sided 95% CIs around the percentiles will be presented. Kaplan-Meier estimates at 3, 6, 9 and 12 months will also be presented. The Kaplan-Meier survival curves will also be presented. For substudy 4 only comparisons between cohorts will be made by considering a hazard ratio, with associated 2-sided 95% confidence interval and p-value, from an unadjusted Cox proportional hazards model.

These analyses will be performed per cohort in substudies 1, 3, 4 and 5 and by dose level in substudy 2. The date of first dose, documented objective tumor response, disease progression, death, last tumor assessment, last contact and DOR days will be reported in a by-patient listing.

6.3.2.3. Progression-Free Survival (All Substudies)

Progression-Free Survival (PFS) will be calculated as the time from cohort assignment by IWRS until disease progression as assessed by BICR, or death from any cause, whichever comes first. Patients who either have no baseline tumor evaluation or have no post- baseline tumor evaluation will be censored at date of cohort assignment by IWRS. Patients without disease progression will be censored at the date of their last tumor evaluation. Patients who discontinue treatment due to reasons other than disease progression by BICR or death will be censored in the PFS analyses as the date of their last tumor evaluation prior to EOT. Patients who progress or die after missing ≥ 2 consecutive scheduled tumor assessments will be censored at the date of the last tumor evaluation prior to progression or death. Any deaths occurring after end of treatment are not taken into account as a PFS event. Patients who stopped treatment without PD will be censored at their last scan prior to end of treatment. For patients with missing end of treatment visit date, a +7 day window compared to the maximum of last dose date, last on treatment visit date will be applied to create a tentative end of treatment visit date and a cut-off for death occurring after this date. The rules for censoring PFS are summarized in the table below:

Table 5: Censoring scheme for PFS

Situation	Date of progression or censoring	Outcome
No baseline or post-baseline tumor assessments	Randomization / Cohort assignment	Censored
Progression documented between scheduled visits	Date of radiological assessment of measured lesions	Progressed
No progression	Date of last radiological assessment of measured lesions	Censored
Treatment discontinuation for reasons other than disease progression by BICR or death	Date of last radiological assessment of measured lesions	Censored
Death before first PD assessment	Date of death	Progressed
Death between adequate assessment visits	Date of death	Progressed
Death or progression after more than one missed tumor assessment or after end of treatment	Date of last radiological assessment of measured lesions prior to progression or death	Censored

Additional sensitivity analyses will be conducted which consider alternative censoring methods as outlined in FDA guidelines ([FDA 2018](#), [FDA 2015](#)).

A first sensitivity analysis will consider the same analysis as outlined in Table 5, but also considering clinical progression as an event (either clinical or radiographic progression will be considered as an event, rather than just radiographic).

A second sensitivity analysis will include all post end of treatment assessments, such that subjects who die or progress after end of treatment will be considered as an event, with censoring at the earliest of last scan performed / new anti-cancer treatment. The censoring scheme for this analysis is outlined in Table 6.

Table 6: Censoring scheme for PFS - sensitivity analysis 2

Situation	Date of progression or censoring	Outcome
No baseline or post-baseline tumor assessments	Randomization / Cohort assignment	Censored
Progression documented between scheduled visits	Date of radiological assessment of measured lesions	Progressed
No progression	Date of last scan performed / new anti-cancer treatment	Censored
Death before first PD assessment	Date of death	Progressed
Death between adequate assessment visits	Date of death	Progressed
Death or progression after more than one missed tumor assessment or after end of treatment	Date of death or progression	Progressed

A third sensitivity analysis (Table 7) uses a conservative approach by assigning the date of discontinuation, or missed visit as an event date.

Table 7: Censoring scheme for PFS - sensitivity analysis 3

Situation	Date of progression or censoring	Outcome
No baseline or post-baseline tumor assessments	Randomization / Cohort assignment	Censored
Progression documented between scheduled visits	Date of radiological assessment of measured lesions	Progressed
No progression, treatment ongoing	Date of last radiological assessment of measured lesions	Censored
Treatment discontinuation for reasons other than disease progression by BICR or death	Date of discontinuation	Progressed
Death before first PD assessment	Date of death	Progressed
Death between adequate assessment visits	Date of death	Progressed
Death or progression after more than one missed tumor assessment or after end of treatment	Date of first missed visit	Progressed

PFS will be analyzed using Kaplan-Meier methodology ([Kaplan & Meier 1958](#)). The median duration of PFS will be presented along with the 2-sided 95% CI. If they are calculable, the 25th and 75th percentiles and

the 2-sided 95% CIs around the percentiles will be presented. Kaplan-Meier estimates at 3, 6, 9 and 12 months will also be presented. The Kaplan-Meier survival curves will also be presented. For substudy 4 comparison between cohorts will be made by considering a hazard ratio, with associated 2-sided 95% confidence interval and p-value, from an unadjusted Cox proportional hazards model.

The date of cohort assignment by IWRS, first dose, disease progression, death, last tumor assessment and PFS days will be reported in a by-patient listing.

